3.7.3.5 Clinical Dementia Rating (CDR) Scale

The CDR is a global scale used at Screening to categorize the severity of Alzheimer's type dementia. It is used to rate the patient's cognitive performance in 6 domains: memory,

orientation, judgment and problem solving, community affairs, home and hobbies, and personal care. Categorical scores for each domain are 0 (none), 0.5 (questionable), 1 (mild), 2 (moderate) and 3 (severe). A summed total score (CDR Sum of Boxes [CDR-SOB]) is produced, and a global score (using the same 5 grades of dementia) is derived. CDR are collected at Screening (all cohorts), Registration/Part 2 (Cohorts A and B only) and Day 449/Part 2 (all cohorts).

In the MAD period, the CDR-SOB at Screening will be summarized as baseline characteristics.

In the LTE and MAD+LTE Periods, CDR-SOB, global score and subdomain scores (actual value, absolute change and percent change from baseline) will be summarized by analysis group and each post-baseline visit at Registration visit (for Cohorts A and B only) and at Day 449 visit.

All CDR collected scores will be presented in data listings for the MAD and MAD+LTE Periods.

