Appendix A A.2. Schedule of Procedures – MAD Part 1, 4-Dose Regimen, Cohorts C and D Continued

| Study Period | Screen | | | | | | | Tr | eatn | | Evalu 3 We | | n Peri | od | | | | | | | | F | Post-Ti (2 | reatme 23 Wee | | iod |
|---|--------------|----|----|----|----|-----|----|-----|------|----|---------------|----|--------|----|----|-----|----|----|----|----|-----|-----------------|---------------|------------------|-----|--------------------------|
| Week | -8 to -1 | | | 1 | | 2 | | 5 | | | 6 | | ę |) | | 10 | | 1 | 3 | | 14 | 17 ¹ | 21 | 25 | 29 | 37 or ET ¹ |
| Day | -57 to -2 | -1 | 1 | 2 | 3 | 8 | 28 | 29 | 30 | 31 | 36 | 56 | 57 | 58 | 59 | 64 | 84 | 85 | 86 | 87 | 92 | 113 | 141 | 169 | 197 | 253 ¹⁵ |
| Visit Window (days)* | - | | | 0 | | ± 3 | | ± ; | 3 | | ± 3 | | ± | 3 | | ± 3 | | ± | 3 | | ± 3 | ± 3 | ± 7 | ± 7 | ± 7 | ± 7 |
| Visit Type ² | cl | cl | cl | cl | ph | cl | cl | cl | cl | ph | cl | cl | cl | cl | ph | ph | cl | cl | cl | ph | ph | cl | cl | cl | cl | cl |
| Structural MRI, safety MRI (GRE T2 star, T2 FLAIR, T2 FSE/TSE, DTI) and ASL | х | | | | | | | | | | | | | | | | | | | | | | | х | | |
| FDG-PET or Tau PET ¹⁴ | Х | | | | | | | | | | | | | | | | | | | | | | | Х | | |
| Imaging of CSF space | Х | | | | | | | | | | | | | | | | | | | | | | | | | |
| FAQ, NPI-Q | Х | Χ | | | | | | | | | | | | | | | | | | | | Х | | Х | | Х |
| RBANS ⁹ | Х | Χ | | | | | | | | | | Х | | | | | | | | | | Х | | Х | | Х |
| MMSE ⁹ | Х | | | | | | | | | | | Х | | | | | | | | | | Х | | Х | | Х |
| MHIS, CDR, GDS-SF | Х | | | | | | | | | | | | | | | | | | | | | | | | | |
| C-SSRS | Х | Χ | Х | | | Х | Х | Х | Х | | Х | Х | Х | Х | | | Χ | Х | Х | | | Х | Х | Х | Х | Х |
| Serum/Plasma Biomarker Sample | | Х | | | | | Х | | | | | Х | | | | | Х | | | | | Х | Х | Х | Х | Х |
| Thyroid Panel | Х | | | | | | | | | | | | | | | | | | | | | | | | | |
| PT, INR, aPTT | Х | Χ | | | | | Х | | | | | Х | | | | | Χ | | | | | Х | Х | Х | Х | Х |
| Archived Serum Sample ¹⁰ | | Χ | | | | | Х | | | | | Х | | | | | Χ | | | | | Х | Х | Х | Х | Х |
| Drug/Alcohol Screen | Х | | | | | | | | | | | | | | | | | | | | | | | | | |
| ECG (12-Lead, triplicate) | Х | Χ | | Χ | | | Х | | | | | Х | | | | | Χ | | | | | Х | | | | Х |
| Adverse Events | Х | Χ | Χ | Χ | Х | Х | Х | Χ | Х | Х | Χ | Х | Х | Х | Х | Х | Χ | Х | Х | Х | Х | Х | Х | Х | Х | Х |

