Appendix A A.4. Schedule of Procedures – LTE Part 2, All Cohorts Continued

| Study Period | Post-Treatment Period (16 Weeks) | |
|--------------------------------------|-------------------------------------|-----------------------|
| Week | 60 | 64 or ET ¹ |
| Day | 421 | 449 |
| Visit Window (days)* | ± 3 | ± 7 |
| Visit Type ² | cl | cl |
| ECG (12-Lead, triplicate) | | X |
| Adverse Events | Х | X |
| Prior/Concomitant Therapy/Procedures | Х | X |
| Serum/Plasma Biomarker | Х | X |
| Archived serum sample ¹¹ | Х | X |
| Plasma sampling for PK | Х | X |
| Plasma Immunogenicity testing | | Х |
| CSF Sample for Biomarker Panel | Х | X ¹³ |
| CSF Samples for PK, Safety | Х | X ¹³ |
| Archived CSF Sample | Х | X ¹³ |

Footnotes are applicable to A.4. Schedule of Procedures

Note: If not specifically labeled, "X" means anytime; ET = early termination

- * Visit windows are calculated relative to Day 1. Note that within each block of visits associated with dose administration, the visits must occur on 4 consecutive days. There are 5 "visit blocks" in Part 2: (Days -1, 1, 2, and 3), (Days 84, 85, 86, and 87), (Days 168, 169, 170, and 171), (Days 252, 253, 254, and 255), and (Days 336, 337, 338, and 339).
- If the patient terminates early from the Treatment Evaluation Period but is willing to participate in the Post-Treatment Period, the patient should complete all visits in the "visit block*" associated with the visit and then proceed to the Week 60 visit approximately 4 weeks after last dose and complete all visits in the Post-Treatment Period. If the patient terminates early from the Treatment Evaluation Period and is not willing to participate in the Post-Treatment Period or if the patient terminates early from the Post-Treatment Period, the patient should complete all visits in the "visit block*" associated with the visit and then proceed to the Week 64 visit as an Early Termination Visit (approximately 4 weeks after the last dose)
- 2 cl = clinic visit; ph = phone visit
- 3 The Registration Visit is not needed for patients who seamlessly move from Part 1 to Part 2 (i.e., patients from Cohorts C and D) as all assessments done at Registration will either be performed during the Part 1, Day 253 visit or during the Part 2, Day -1 visit

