1.1 Study Overview

This is a Phase 1, multi-center, double-blind, randomized, placebo-controlled study of multiple IT bolus administrations of ISIS 814907 in patients with mild Alzheimer's Disease (AD) aged 50-74 years, inclusive.

This study is divided into 2 parts:

- Part 1: a randomized, double-blind, placebo-controlled multiple ascending dose (MAD) part, comprising a Screening Period of 8 weeks, a Treatment Evaluation Period of 13 weeks, and a Post-Treatment Period of 23 weeks
- Part 2: an open-label, long-term extension (LTE) part, comprising a Registration Period of 3 weeks (only for those who cannot transition seamlessly, i.e., patients from Cohorts A and B), a Treatment Evaluation Period of 48 weeks, and a Post-Treatment Period of 16 weeks (except in the UK (Amendment 7) where the Post-Treatment Period is 23 weeks)
 - o For patients participating in Cohorts A and B there will be a variable gap of time between the end of Part 1 and entry into Part 2
 - Patients participating in Cohorts C and D will seamlessly transition from Part 1 to Part 2. Day 253 in Part 1 (i.e., last visit of Part 1 Post-Treatment Period) will correspond to Day -1 in Part 2 (i.e., first visit of Part 2 Treatment Evaluation Period).

Multiple Ascending Dose, Part 1

Four (4) ascending dose level cohorts (A, B, C, and D) of patients were enrolled sequentially and randomized with an overall ratio of 3:1 to receive ISIS 814907 or placebo. A sentinel dosing strategy was implemented. The first 2 patients at a given dose level were assigned 1:1 active: placebo, and at least 1 week elapsed between initiation of treatment in these 2 patients and initiation of treatment in additional patients at this dose level. The remaining patients were assigned to active or placebo at a 5:1 ratio for cohorts with N = 8, 8:2 ratio for cohorts with N = 12, or 11:3 ratio for cohorts with N = 16 to ensure a 3:1 active: placebo balance in each cohort. Based on the profile of effects observed in non-human primate toxicology studies, 24 hours is expected to be a sufficiently long observation period to identify possible safety

issues. Thus, as a safety measure, the sentinel dosing algorithm utilized for this study required that 1-week elapsed between initiation of treatment in the first 2 patients and initiation of treatment in subsequent patients in the cohort. Identified and potential risks associated with ISIS 814907 are described in detail in the Investigator's Brochure.

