3.2.3.2 Active treatment period baseline

Active treatment period baseline will be used to analyze the LTE Period and the Active Treatment Period. Active treatment period baseline is the same as the MAD baseline for early start subjects, and for late start subjects is the last non-missing measure collected prior to the first dose of study drug in the LTE except in the instances below:

- o For vital signs (blood pressure [BP] and heart rate [HR]), as the average of the triplicate values collected on Day 1 pre-dose in the LTE. If only one or two assessments are available, the single assessment or average of the two assessments will be used.
- For ECG continuous parameters, as the average of the triplicate values collected immediately prior to first dose in the LTE. For ECG interpretation, baseline will be defined as the worst categorical results of the triplicate results collected immediately prior to first dose in the LTE.
- For C-SSRS suicidal ideation score, as the maximum score collected on Day -1 and Day 1 pre-dose in the LTE.

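### As scheduled, late-start Cohort C and D patients' LTE-Period CDR change runs from MAD Screening, 36 to 44 weeks before any active dose, and Late Start A+B+C averages two different intervals

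*Combined protocol and SAP*

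**What the plan says.** **Collection times.** SAP 3.7.3.5 has every cohort rated at MAD Screening and, after that, only at "Registration/Part 2 (Cohorts A and B only) and Day 449/Part 2 (all cohorts"). The protocol grids agree. Appendix A.2 (row "MHIS, CDR, GDS-SF") and Appendix A.3 mark CDR at Screening only. Appendix A.4 marks it at Registration and Day 449, not at Day -1.

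**Baseline rule.** SAP 3.2.3.2 says that "Active treatment period baseline will be used to analyze the LTE Period and the Active Treatment Period". For early starters this equals the MAD baseline; "for late start subjects is the last non-missing measure collected prior to the first dose of study drug in the LTE". Exceptions follow for vital signs, ECG and C-SSRS, but none for CDR. Table B1 gives the baseline reference as prior to LTE for placebo patients in all four cohorts.

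**Output.** SAP 3.7.3.5: "In the LTE and MAD+LTE Periods, CDR-SOB, global score and subdomain scores (actual value, absolute change and percent change from baseline) will be summarized". Results are broken down per group, for Registration (A and B) and Day 449. Under SAP 3.2.2.2, Cohort C placebo patients are pooled with those from A and B, and Cohort D placebo patients stand alone.

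**Text pointing the other way.** Footnote 3 of Appendix A.4 says that for Cohorts C and D no Registration Visit is needed because "all assessments done at Registration will either be performed during the Part 1, Day 253 visit or during the Part 2, Day -1 visit".

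**The concern.** A reader of the LTE-Period table, told that the baseline is the active-treatment one and precedes the LTE, will take a late starter's change as change since starting drug. For Cohort C and D placebo patients it would also contain screening time, the placebo dosing period and the Part 1 follow-up. Any worsening over that time would appear in the LTE column.

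The problem is specific to CDR. FAQ, NPI-Q, RBANS and MMSE are all scheduled at Part 1 Day 253, so C/D late starters have an LTE-entry value for each of them. CDR is also one of the clinical scales that SAP 3.2.1 selects for the MAD+LTE analysis, so it is not a marginal measure.

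At stake is how three things are read: the pooled Late Start A+B+C column, comparisons between late-start groups, and late-start or pooled LTE columns taken as change since first active dose.

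**Working it through.** **The plan's own figure.** Protocol 3.4 gives Part 1 as approximately 44 weeks. The period lengths reproduce it: 8 + 13 + 23 = 44 weeks, or 36 without Screening.

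**Inputs**
- MAD Screening window: Day -57 to Day -2 (Part 1 schema; Appendix A).
- Link between parts for C/D: "Day 253 in Part 1 (i.e., last visit of Part 1 Post-Treatment Period) will correspond to Day -1 in Part 2" (SAP 1.1), so LTE Day 1 is MAD Day 254.
- Registration window for A/B: Day -21 to Day -2 (Part 2 schema).
- Final CDR: LTE Day 449.
- Cohort sizes 8, 8, 12 and 16 at 3:1 (synopsis; protocol 3.1.1), so planned placebo is A 2, B 2, C 3 and D 4, 11 in all.

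**Intervals.** There is no Day 0, so the gap from Day -k to Day d is k + d - 1 days.
- C/D, Screening to LTE Day 1: 2 + 254 - 1 = 255 days to 57 + 254 - 1 = 310 days, i.e. 36.4 to 44.3 weeks. With the ±7-day window on Day 253 this becomes 248 to 317 days, 35.4 to 45.3 weeks.
- LTE Day 1 to Day 449: 448 days = 64 weeks.
- A/B, Registration to LTE Day 1: 2 to 21 days, i.e. 0.3 to 3.0 weeks.

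| Late starters | Baseline CDR as scheduled | Baseline to Day 449 | Share before first active dose |
|---|---|---|---|
| A, B | LTE Registration | 450 to 469 days (64.3 to 67.0 weeks) | 2/450 = 0.4% to 21/469 = 4.5% |
| C, D | MAD Screening | 703 to 758 days (100.4 to 108.3 weeks) | 255/703 = 36% to 310/758 = 41% |

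The C/D interval is 703/448 = 1.57 to 758/448 = 1.69 times the 64-week LTE interval.

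**Patients affected, at planned sizes with full rollover**
- Late Start A+B+C: 3 of 7. The column's mean interval is (4 × 450 + 3 × 703)/7 = 558 days (79.8 weeks) to (4 × 469 + 3 × 758)/7 = 593 days (84.7 weeks), which describes neither subgroup.
- Late Start D: 4 of 4. MAD Screening is the baseline under both rules, so the Day 449 CDR change is the same in the LTE and MAD+LTE tables.
- Overall: 7 of 11 placebo patients.

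**Illustration only.** The documents give no rate of CDR-SOB decline. Assuming a steady 1 to 2 points a year, the time before first active dose would contribute 255/365.25 × 1 = 0.7 to 310/365.25 × 2 = 1.7 points. The LTE itself would contribute 448/365.25 × 1 = 1.2 to 448/365.25 × 2 = 2.5 points.

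**A related slip.** SAP 3.7.3.5 lists Registration as a post-baseline visit for A/B. For late-start A/B patients it is the LTE baseline, so the LTE-Period change there is zero by construction.

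**The case against.** Five points can be made on the other side.

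1. **Early versus late comparisons.** A reader might infer that the treatment groups in general are not comparable. The documents do not support that. Early starters' LTE baseline is also the MAD baseline, so Early and Late Start D cover the same 100 to 108 weeks, as do Early Start C and Cohort C placebo. This stands and limits the point to the uses named above.

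2. **Purpose of the table.** A reader might infer that the LTE table is meant to estimate decline on drug. No section says so. SAP 1.2.3 includes progression markers primarily as a safety measure, the CDR summaries are descriptive with no test, and early starters' LTE-Period change includes Part 1 by design. This stands, but the active-treatment and prior-to-LTE labels still invite the reading.

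3. **A common-baseline summary exists.** SAP 3.2.3.1 gives the MAD+LTE Period the MAD baseline for every group, and CDR is reported there. Actual values and listings are planned too. This stands: only the LTE-Period summary is affected.

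4. **An entry CDR may exist.** Footnote 3 says the Registration assessments are done at Day 253 or Day -1 for C/D, and SAP 3.2.4 lets an unscheduled result set baseline. It cannot be taken as settled that these patients have no entry CDR. Against this, footnote 15 to Appendix A.2 and A.3 requires only assessments listed at those two visits; CDR is listed at neither, and SAP 3.7.3.5 follows the grids. The passages conflict.

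5. **Numbers affected.** The protocol synopsis allows fewer patients into Part 2 than Part 1, so 7 of 11 rests on planned sizes and complete rollover. This stands.

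**Conclusion.** The point holds under the schedule grids and the SAP as written. A baseline described as prior to LTE is, for Cohort C and D placebo patients' CDR, a MAD Screening value. Their reported LTE change therefore includes 36 to 44 weeks without active drug, and Late Start A+B+C averages intervals of about 64 to 67 and 100 to 108 weeks.

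It depends on no CDR having been rated at Day 253, Day -1 or an unscheduled visit before the first LTE dose; if one was, the distortion disappears for that patient. The patient counts assume planned sizes and full rollover. The size in CDR-SOB points rests wholly on an assumed rate of decline. The conclusion does not extend to early versus late within C or D, to the MAD+LTE summary, or to any hypothesis test. It concerns one exploratory, descriptive output that would mislead as labelled.

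**What to change.** 1. Reconcile footnote 3 of Appendix A.4 with the grids in A.2 to A.4, footnote 15 and SAP 3.7.3.5, and establish whether a Day 253 or Day -1 CDR was collected in Cohorts C and D.
2. If it was, correct the collection statement in SAP 3.7.3.5 and use that value as the late-start baseline.
3. If it was not, amend SAP 3.7.3.5 so that Cohort C late starters are not pooled with A/B for LTE-Period CDR change. Show late-start C and D actual values in the LTE Period. Report their change from MAD baseline, in the MAD+LTE summary, labelled as such and with elapsed time stated.
4. Stop listing Registration as a post-baseline LTE visit for late-start A/B patients.

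**Cost.** SAP wording only, with no added assessment. One descriptive change column would shrink: late-start A/B would hold at most four planned patients, and late-start C and D would drop out of the LTE-Period change table. The time-matched early versus late comparison within D remains available in the MAD+LTE summary.

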5. APPENDIX

Table A1: ROIs for Volumetric Analysis

| ROI Name | ROI Description |
|---------------------------|---------------------------------|
| INTRACRANIAL ^a | Total Intracranial Volume (ICV) |
| HIPPOCAMPUS_RIGHT | Hippocampus right |
| HIPPOCAMPUS_LEFT | Hippocampus left |
| HIPPOCAMPUS * | Hippocampus |
| VENTRICLE_LATERAL_RIGHT | Lateral Ventricle right |
| VENTRICLE_LATERAL_LEFT | Lateral Ventricle left |
| THIRD_VENTRICLE | 3 rd Ventricle |
| FOURTH_VENTRICLE | 4 th Ventricle |
| BRAIN_VENTRICLE ** | All ventricles |
| WHOLE_BRAIN | Whole brain |

Table A2: ROIs for Perfusion and PET Analyses

| ROI Name | ROI Description | Composite | | |
|----------------------------------|--------------------------------|---------------------|--|--|
| FRONTAL_LOBE_MIDDLE_L | Middle frontal gyrus left | | | |
| FRONTAL_LOBE_MIDDLE_R | Middle frontal gyrus right | | | |
| FRONTAL LOBE PRECENTRAL L | Precentral gyrus left | | | |
| FRONTAL_LOBE_PRECENTRAL_R | Precentral gyrus right | | | |
| FRONTAL LOBE STRAIGHT GYRUS L | Straight gyrus left | | | |
| FRONTAL_LOBE_STRAIGHT_GYRUS_R | Straight gyrus right | | | |
| ORBITOFRONTAL_CORTEX_ANTERIOR_L | Anterior orbital gyrus left | | | |
| ORBITOFRONTAL_CORTEX_ANTERIOR_R | Anterior orbital gyrus right | | | |
| FRONTAL_LOBE_INFERIOR_L | Inferior frontal gyrus left | Frontal Composite | | |
| FRONTAL_LOBE_INFERIOR_R | Inferior frontal gyrus right | | | |
| FRONTAL_LOBE_SUPERIOR_L | Superior frontal gyrus left | | | |
| FRONTAL_LOBE_SUPERIOR_R | Superior frontal gyrus right |] | | |
| ORBITOFRONTAL_CORTEX_MEDIAL_L | Medial orbital gyrus left | | | |
| ORBITOFRONTAL_CORTEX_MEDIAL_R | Medial orbital gyrus right | | | |
| ORBITOFRONTAL_CORTEX_LATERAL_L | Lateral orbital gyrus left | | | |
| ORBITOFRONTAL_CORTEX_LATERAL_R | Lateral orbital gyrus right | | | |
| ORBITOFRONTAL_CORTEX_POSTERIOR_L | Posterior orbital gyrus left | | | |
| ORBITOFRONTAL_CORTEX_POSTERIOR_R | Posterior orbital gyrus right | | | |
| CINGULATE_SUBGENUAL_ANTERIOR_L | Subgenual frontal cortex left | Cingulate Composite | | |
| CINGULATE_SUBGENUAL_ANTERIOR_R | Subgenual frontal cortex right | Cingulate Composite | | |

^a ROI will only be calculated for baseline/screening scans

* Total Hippocampal Volume is calculated by adding up the volumes of Hippocampus right and Hippocampus left.

** Total Brain Ventricular Volume is calculated by adding up the volumes of Lateral Ventricle right, Lateral Ventricle left, 3rd Ventricle and 4th Ventricle.

| SUBCALLOSAL AREA L | Subcallosal area left | |
|------------------------------------|---|---------------------------|
| SUBCALLOSAL AREA R | Subcallosal area right | |
| CINGULATE PRESUBGENUAL ANTERIOR L | Pre-subgenual frontal cortex left | |
| CINGULATE PRESUBGENUAL ANTERIOR R | Pre-subgenual frontal cortex right | |
| CINGULATE ANTERIOR L | Cingulate gyrus anterior part left | |
| CINGULATE ANTERIOR R | Cingulate gyrus anterior part right | |
| CINGULATE POSTERIOR L | Gyrus cinguli posterior part left | |
| CINGULATE POSTERIOR R | Gyrus cinguli posterior part right | |
| HIPPOCAMPUS L | Hippocampus left | |
| HIPPOCAMPUS R | Hippocampus right | |
| TEMPORAL LOBE ANTERIOR MEDIAL L | Anterior temporal lobe medial part left | |
| TEMPORAL LOBE ANTERIOR MEDIAL R | Anterior temporal lobe medial part right | M. E. T. T |
| TEMPORAL_LOBE_ANTERIOR_LATERAL_L | Anterior temporal lobe lateral part left | Medial Temporal Composite |
| TEMPORAL_LOBE_ANTERIOR_LATERAL_R | Anterior temporal lobe lateral part right | |
| PARAHIPPOCAMPAL_L | Parahippocampal and ambient gyri left | |
| PARAHIPPOCAMPAL R | Parahippocampal and ambient gyri right | |
| TEMPORAL_LOBE_SUPERIOR_POSTERIOR_L | Superior temporal gyrus posterior part left | |
| TEMPORAL_LOBE_SUPERIOR_POSTERIOR_R | Superior temporal gyrus posterior part right | |
| TEMPORAL_LOBE_MIDDLE_INFERIOR_L | Middle and inferior temporal gyrus left | |
| TEMPORAL LOBE MIDDLE INFERIOR R | Middle and inferior temporal gyrus right | |
| FUSIFORM GYRUS L | Fusiform gyrus left | T 1.0 ' |
| FUSIFORM GYRUS R | Fusiform gyrus right | Temporal Composite |
| TEMPORAL LOBE POSTERIOR L | Posterior temporal lobe left | |
| TEMPORAL LOBE POSTERIOR R | Posterior temporal lobe right | |
| TEMPORAL LOBE SUPERIOR ANTERIOR L | Superior temporal gyrus anterior part left | |
| TEMPORAL LOBE SUPERIOR ANTERIOR R | Superior temporal gyrus anterior part right | |
| PARIETAL LOBE POSTCENTRAL L | Postcentral gyrus left | |
| PARIETAL LOBE POSTCENTRAL R | Postcentral gyrus right | |
| PARIETAL LOBE SUPERIOR L | Superior parietal gyrus left | Paristal Community |
| PARIETAL_LOBE_SUPERIOR_R | Superior parietal gyrus right | Parietal Composite |
| PARIETAL_LOBE_INFERIORLATERAL_L | Inferiolateral remainder of parietal lobe left | |
| PARIETAL_LOBE_INFERIORLATERAL_R | Inferiolateral remainder of parietal lobe right | |
| OCCIPITAL LOBE LATERAL L | Lateral remainder of occipital lobe left | |
| OCCIPITAL_LOBE_LATERAL_R | Lateral remainder of occipital lobe right | |
| OCCIPITAL LOBE LINGUAL GYRUS L | Lingual gyrus left | Occipital Composite |
| OCCIPITAL_LOBE_LINGUAL_GYRUS_R | Lingual gyrus right | — Composite |
| OCCIPITAL_LOBE_CUNEUS_L | Cuneus left | |
| OCCIPITAL_LOBE_CUNEUS_R | Cuneus right | |

Table A3: ROIs for Diffusion Analysis

| ROI Name | ROI Description |
|----------------------|---|
| CINGULUM HIPPOCAMPUS | Cingulum and hippocampus left and right |
| FORCEPS_MAJOR | Forceps major (posterior forceps) |
| FORNIX | Fornix |

Table B1: LTE Period: Analysis Groups and Baseline Definition

| Baseline reference [1] | Cohort | MAD period treatment | LTE period treatment [2] | Late start ABC | Late start D | Early start A | Early start B | Early start C | Early start D | ISIS 814907 60 mg Q12W [3] | ISIS 814907 115 mg Q12W | All Roll- over |
|---------------------------|--------|----------------------------|----------------------------|-------------------|-----------------|------------------|------------------|------------------|------------------|-------------------------------------|----------------------------------|-------------------|
| | A | Placebo | ISIS 814907 60 mg q12w | X | | | | | | X | | X |
| prior to LTE | В | Placebo | ISIS 814907 60 mg q12w | X | | | | | | X | | X |
| prior to LTE | C | Placebo | ISIS 814907 60 mg q12w | X | | | | | | X | | X |
| | D | Placebo | ISIS 814907 115 mg q12w | | X | | | | | | X | X |
| | A | ISIS 814907 10 mg q4w | ISIS 814907 60 mg q12w | | | X | | | | X | | X |
| prior to MAD | В | ISIS 814907 30 mg q4w | ISIS 814907 60 mg q12w | | | | X | | | X | | X |
| prior to MAD | С | ISIS 814907 60 mg q4w | ISIS 814907 60 mg q12w | | | | | X | | X | | X |
| | D | ISIS 814907 115 mg q12w | ISIS 814907 115 mg q12w | | | | | | X | | X | X |

Note: In case of very few subjects, the analysis groups may be pooled.

^[1] Please refer to Section 3.2.2 and 3.2.3 for details and exceptional instances.
[2] As indicated by the orange highlighting, only the LTE period (and relevant baseline) data will contribute to the analysis.

^[3] Select analyses only.

Table B2: MAD+LTE Period: Analysis Groups and Baseline Definition

| Baseline reference [1] | Cohort | MAD period treatment [2] | LTE period treatment [2] | Late start ABC | Late start D | Early start A | Early start B | Early start C | Early start D |
|------------------------|--------|----------------------------|----------------------------|-------------------|-----------------|------------------|------------------|------------------|------------------|
| | A | Placebo | ISIS 814907 60 mg q12w | X | | | | | |
| | В | Placebo | ISIS 814907 60 mg q12w | X | | | | | |
| | С | Placebo | ISIS 814907 60 mg q12w | X | | | | | |
| prior to MAD | D | Placebo | ISIS 814907 115 mg q12w | | X | | | | |
| prior to MAD | A | ISIS 814907 10 mg q4w | ISIS 814907 60 mg q12w | | | X | | | |
| | В | ISIS 814907 30 mg q4w | ISIS 814907 60 mg q12w | | | | X | | |
| С | С | ISIS 814907 60 mg q4w | ISIS 814907 60 mg q12w | | | | | X | |
| | D | ISIS 814907 115 mg q12w | ISIS 814907 115 mg q12w | | | | | | X |

^[1] Please refer to Section 3.2.2 and 3.2.3 for details and exceptional instances.

Note: In case of very few subjects, the analysis groups may be pooled.

^[2] As indicated by the orange highlighting, data from both the MAD and LTE periods will contribute to the analysis.

Table B3: Active Treatment Period: Analysis Groups and Baseline Definitions

| Baseline reference [1] | Cohort | MAD period treatment [2] | LTE period treatment [2] | Late start ABC | Late start D | Early start | Early start B | Early start C | Early start D | ISIS 814907 115mg Q12W | Total Active |
|------------------------|--------|----------------------------|----------------------------|-------------------|-----------------|-------------|------------------|------------------|------------------|---------------------------------|-----------------|
| | A | Placebo | ISIS 814907 60 mg q12w | X | | | | | | | X |
| naisa ta LTE | В | Placebo | ISIS 814907 60 mg q12w | X | | | | | | | X |
| prior to LTE | С | Placebo | ISIS 814907 60 mg q12w | X | | | | | | | X |
| | D | Placebo | ISIS 814907 115 mg q12w | | X | | | | | X | X |
| | A | ISIS 814907 10 mg q4w | ISIS 814907 60 mg q12w | | | X | | | | | X |
| prior to MAD | В | ISIS 814907 30 mg q4w | ISIS 814907 60 mg q12w | | | | X | | | | X |
| F | С | ISIS 814907 60 mg q4w | ISIS 814907 60 mg q12w | | | | | X | | | X |
| F11 Diagram Contact | D | ISIS 814907 115 mg q12w | ISIS 814907 115 mg q12w | | | | | | X | X | X |

^[1] Please refer to Section 3.2.2 and 3.2.3 for details and exceptional instances.

Note: In case of very few subjects, the analysis groups may be pooled.

